4.6 Stratification Factors and Treatment Assignments

4.6.1 Stratification Factors

1) Platinum Status: Ineligible vs. Refractory

- Platinum ineligible is defined as meeting any one of the following criteria: Impaired renal function [creatinine clearance (CrCl) of <30 mL/min], >2 peripheral neuropathy, or NYHA Heart Failure of >3.
- Platinum-refractory is defined as prior platinum-based perioperative chemotherapy within 12 months of relapse or prior platinum-based chemotherapy for metastatic disease.

2) Visceral Metastasis: Yes vs. No

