4.6.2 Treatment Assignments

Patients will be randomized 1:1 to the two treatment arms. The factors defined in [Section 4.8.1](#) will be used as stratification factors.

After the patient has been registered into the study, the values of the stratification factors will be recorded, and the patient will be randomized to one of the following treatment groups using the Pocock and Simon dynamic allocation procedure which balances the marginal distributions of the stratification factors between the treatment groups.

- 1) Immunotherapy
- 2) Immunotherapy + Single Site Radiotherapy

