13.6 Primary Analysis Plan

Interim analysis for futility: There will be one interim analyses for futility. The interim analysis will occur after 50% of the patients (i.e. 68) have been followed for six months. If at this time the tumor response for Arm A (immunotherapy alone) is greater than the tumor response rate for Arm B (immunotherapy plus radiation), which would correspond to an OR > 1, the recommendation will be to stop the trial due to futility.

Final Analysis: The final analysis will occur after 136 evaluable patients have completed 6 months of follow-up. The tumor response rate will be analyzed with a Mantel-Haenszel test (that accounts for the randomization stratification factors) comparing the response rates between the two treatment arms. The analysis will be a modified intent-to-treat analysis where patients are ineligible or not evaluable will be excluded. An additional analysis will be conducted using logistic regression analysis that includes treatment arm and any baseline variables that are imbalanced between the arms as explanatory variable.

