13.7 Secondary Analysis Plans

A key secondary analysis will be to repeat the primary analysis that defines a tumor response by central review using iRECIST criteria.

For the secondary time-to-event endpoints, stratified Cox models will be used to compare the outcomes between the two treatment groups. This includes PFS and OS. The subgroup analyses will be done using a stratified Cox model that includes the treatment arm assignment as an explanatory variable and a separate model will be generated for each level for the subgroup of interest. The results will be summarized with a forest plot displaying the estimate of the hazard ratio and corresponding 95% confidence interval.

The rates of treatment discontinuation at one year will be summarized with a binomial point estimate and corresponding 95% confidence interval by arm. The denominator will be all patients randomized to the treatment arm and who are still alive and progression-free at one year and the numerator will be the number of patients who are alive and progression-free at one year and discontinued the protocol

treatment prior to one year. A comparison between the rates will be performed with a chi-square test or a Fisher's exact test if the assumptions of the chi-square test are violated.

Adverse events will be summarized with frequencies and relative frequencies. The maximum grade for an AE will be recorded for each patient by treatment arm. The number (percent) of patients that experience each observed adverse event will be summarized by treatment arm. In addition, the proportion of patients that experience a grade 3+, grade 4+, and grade 5 adverse event will be summarized as the number and percent of patients by treatment arm. The primary summary will be regardless of attribution. We will also do an analogous summary of the adverse events that were deemed at least possibly related to treatment.

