To evaluate between-arm differences in patient-reported adverse events as assessed by the PRO-CTCAE from baseline through 24 months, the frequency and proportion of patients with a maximum post-baseline score greater than 0 will be compared across arms using a χ^2 test or Fisher's exact test with a nominal significance level of $\alpha = .10$. Similarly, the frequency and proportion of patients with a maximum post-baseline score greater than or equal to 3 will be compared across arms using a χ^2 test or Fisher's exact test with a nominal significance level of $\alpha = .10$. The same procedure will be applied to patients' maximum baseline-adjusted scores. Patients' maximum baseline-adjusted scores will be calculated using the method described by Dueck et al. If the patient's maximum post-baseline score is greater than his/her baseline score, then the patient's maximum baseline-adjusted score will equal his/her maximum post-baseline score; otherwise, if the patient's maximum post-baseline score is less than or equal to his/her baseline score, then the patient's maximum baseline-adjusted score will equal 0. The aforementioned analyses will be based on all available PRO-CTCAE data. However, the proportion of, and reported reasons for, missing data will be presented by time point and arm. Correlation analysis and logistic regression analysis will be used to examine whether baseline patient characteristics and prognostic factors predict missingness. As a sensitivity analysis, multiple imputation may be performed to assess the robustness of results across different assumptions about the missing data. Since a preferred or optimal statistical methodology for PRO-CTCAE data is yet to be determined, additional analyses of PRO-CTCAE data beyond those specified above may be undertaken based on the current state of the science at time of data maturity for this study.

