14.1.4 Statistical Considerations

All questionnaires will be scored according to published scoring algorithms, including recommendations for addressing missing items within a scale. An intent-to-treat approach will be used for all analyses. To evaluate between-arm differences in patient-reported fatigue from baseline through 24 months, the area under the curve will be calculated as a summary statistic for each arm based on estimates from a mixed model for patient-reported fatigue as assessed by the PROMIS-Fatigue 8a at baseline, at 45 days, and at 6, 12, and 24 months. This approach of estimating each arm's area under the curve as a summary statistic (rather than each patient's area under the curve as a summary measure) is recommended for addressing missing data over time²⁷. The mixed model will include a fixed intercept; fixed effect for time, arm, and arm by time interaction; and residual covariance matrix based on the observed covariances. An unstructured residual covariance matrix will initially be used, though alternative structures will be investigated with final selection based on convergence of the mixed model and minimization of the Akaike information criterion. Stratification factors used in the randomization as well as baseline patient characteristics and prognostic factors may be included in the mixed model as covariates. Estimates from the mixed model will be used to construct a 90% confidence interval for the difference in area under the curve between arms. The contrast estimated via the mixed model will involve a two-sided *t*-test with a nominal significance level of $\alpha = .10$.

To evaluate between-arm differences in HRQOL from baseline through 24 months, the area under the curve will be calculated as a summary statistic for each arm based on estimates from a mixed model for HRQOL as assessed by the EORTC QLQ-C30 at baseline, at 45 days, and at 6, 12, and 24 months. Estimates from the mixed model will be used to construct a 90% confidence interval for the difference in area under the curve between arms. The contrast estimated via the mixed model will involve a two-sided *t*-test with a nominal significance level of $\alpha = .10$.

To evaluate between-arm differences in urinary symptoms from baseline through 24 months for patients with a urostomy, the area under the curve will be calculated as a summary statistic for each arm based on estimates from a mixed model for urinary symptoms as assessed by the

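### PRO-CTCAE tests are unstratified and the QOL mixed models leave the minimisation factors optional; if those factors are prognostic, these comparisons lose a little precision

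*Combined protocol and SAP*

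**What the plan says.** - **Allocation (4.6.1, 4.6.2).** The factors are "Platinum Status: Ineligible vs. Refractory" and "Visceral Metastasis: Yes vs. No". Allocation is 1:1 by the "Pocock and Simon dynamic allocation procedure which balances the marginal distributions of the stratification factors between the treatment groups".
- **Response (13.6).** "The tumor response rate will be analyzed with a Mantel-Haenszel test (that accounts for the randomization stratification factors"). Section 13.7 repeats this analysis with iRECIST response.
- **PFS and OS (13.7).** Stratified Cox models.
- **PRO-CTCAE (13.7).** "the frequency and proportion of patients with a maximum post-baseline score greater than 0 will be compared across arms using a" chi-square or Fisher's exact test at a nominal alpha of 0.10. The same test is used for scores of 3 or more and for baseline-adjusted scores. Stratification is not mentioned, and no between-arm interval is planned.
- **QOL mixed models (14.1.4).** "Stratification factors used in the randomization as well as baseline patient characteristics and prognostic factors may be included in the mixed model as covariates". This sentence stands in the fatigue paragraph; the paragraphs on the other scales name no covariates. Each model yields a 90% interval and a two-sided test at 0.10 for the between-arm contrast. The Akaike criterion is given only for choosing the covariance structure, not the covariates.

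**The concern.** Minimisation removes most of the between-arm variation that comes from the two factors. An analysis that leaves them out still counts that variation in its standard error. When the factors predict the outcome, the standard error is therefore too large, the test rejects too seldom under the null, and power is lost. The plan avoids this for response, PFS and OS, but gives no reason for a different approach to PRO-CTCAE and QOL.

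The QOL text raises a second problem that does not depend on prognostic strength. It leaves open whether the stratification factors, baseline characteristics and unnamed prognostic factors enter the model. The trial is open-label (13.1), so the covariate set could be settled after data have been seen.

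A prognostic link is plausible, though this is inference: platinum ineligibility is defined by renal impairment, neuropathy or heart failure (4.6.1), which could bear on fatigue, dyspnea or pain scores. Section 14.1.2 hypothesises worse fatigue and symptoms with radiotherapy, so a conservative comparison makes the hypothesised harm somewhat harder to show.

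**Working it through.** **Inputs from the plan.** QOL (14.1.4): 120 evaluable patients, 5 assessments, intraclass correlation 0.50, standardised difference 0.35, two-sided alpha 0.10, stated power 80%. Parent trial (13.4): 136 evaluable patients.

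**Assumed, because the documents do not give them.** The share R² of outcome variance explained by the two factors; the odds ratio per factor for binary outcomes; factor prevalences of 30% and 60%; a biased-coin probability of 0.8.

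**Step 1: the stated QOL power.** The mean of 5 assessments has SD √((1 + 4 × 0.50)/5) = √0.6 = 0.775. With 60 per arm, the standard error is 0.775 × √(2/60) = 0.1414. The standardised effect is 0.35/0.1414 = 2.475, so power = Φ(2.475 − 1.645) = Φ(0.830) = 79.7%. The stated 80% reproduces.

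**Step 2: QOL contrasts.** If the balanced factors explain a share R² of the variance:

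- excess width of the unadjusted interval = 1/√(1 − R²) − 1
- true size of the unadjusted test = 2 × [1 − Φ(1.645/√(1 − R²))]
- unadjusted power = Φ((2.475 − 1.645)/√(1 − R²))
- adjusted power = Φ(2.475/√(1 − R²) − 1.645)

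| R² | Interval too wide by | True size at nominal 0.10 | Power, unadjusted | Power, adjusted |
|---|---|---|---|---|
| 0 | 0% | 0.100 | 79.7% | 79.7% |
| 2% | 1.0% | 0.097 | 79.9% | 80.4% |
| 5% | 2.6% | 0.091 | 80.3% | 81.4% |
| 10% | 5.4% | 0.083 | 80.9% | 83.2% |
| 20% | 11.8% | 0.066 | 82.3% | 86.9% |

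The gain from adjustment is the difference between the last two columns: 81.4 − 80.3 = 1.1 points at R² = 5% and 83.2 − 80.9 = 2.3 points at 10%. Comparing adjusted power with the stated 80% would overstate the gain, because minimisation also raises the power of the unadjusted test.

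**Step 3: PRO-CTCAE-type proportions.** Pocock-Simon minimisation was simulated with 136 patients, an event rate near 50%, a treatment odds ratio of 2.25 for power, and 6,000 trials per row. The test was two-sided at nominal 0.10. Monte Carlo error is about 0.4 points for size and 0.6 for power.

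| Odds ratio per factor | Size, chi-square | Size, stratified Mantel-Haenszel | Power, chi-square | Power, stratified Mantel-Haenszel |
|---|---|---|---|---|
| 1 | 0.107 | 0.104 | 75.8% | 75.1% |
| 1.5 | 0.107 | 0.107 | 75.3% | 75.1% |
| 2 | 0.095 | 0.099 | 73.2% | 73.9% |
| 3 | 0.079 | 0.096 | 69.8% | 72.2% |
| 5 | 0.067 | 0.095 | 61.0% | 67.2% |

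Up to an odds ratio of about 2 the two tests are practically the same. At 3 and 5 the chi-square test loses 72.2 − 69.8 = 2.4 and 67.2 − 61.0 = 6.2 points of power.

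**The case against.** **Strength is unknown.** Nothing in the documents shows that platinum status or visceral metastasis predicts patient-reported symptoms. An odds ratio of 3 for each factor means 9 for the two combined. This stands: the size of the effect is conditional, and with weak factors it is negligible.

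**These analyses are secondary and nominal-alpha.** Unstratified tests remain valid here. PRO-CTCAE is not the safety instrument: section 9.0 makes clinician-graded CTCAE the safety standard and bars protocol action on PRO-CTCAE, and section 13.7 says that the best method for PRO-CTCAE data is unsettled and allows further analyses. This also stands and lowers the priority. A reader might infer that a safety signal would be hidden, but safety monitoring in 13.8 rests on grade 3 or higher CTCAE rates.

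**Balance may erode in the QOL set.** Participation is optional, the plan allows 15% to decline or miss booklets, and follow-up runs to 24 months, while section 1.1 cites a median survival of 10.3 months on pembrolizumab. Erosion would bring the unadjusted size back toward 0.10, so the sizes in Step 2 are the conservative extreme. It was not simulated for QOL. Adjustment for prognostic factors would still narrow the interval.

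**The 1-year discontinuation test.** Section 13.7 also says "A comparison between the rates will be performed with a chi-square test", or Fisher's test, so a reader might extend the point to it. The documents do not support that. The denominator is restricted to patients who reach one year alive and without progression. In a simulation with allocation balanced within the four strata and assumed 1-year rates of 15% to 30%, about 29 to 32 patients remained. The SD of the between-arm imbalance in a factor rose from about 0.01 as randomised to about 0.17 in that subset, and the chi-square size at nominal 0.05 was 0.044 to 0.053. Minimisation balance does not carry over, so there is little or no conservatism to correct.

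**Conclusion.** The point holds as a minor one. The PRO-CTCAE tests omit the minimisation factors, and the QOL models leave them optional with no selection rule, unlike the response, PFS and OS analyses. The open covariate choice is a prespecification gap at any prognostic strength. The loss of precision is conditional: QOL intervals about 1% to 5% too wide for R² of 2% to 10%, and no material effect on the PRO-CTCAE tests until the odds ratio per factor exceeds about 2. All of this rests on assumed prognostic strength, prevalences and coin probability.

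Three stronger readings are not supported:

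- *The results would be anti-conservative.* The direction is the opposite. The chi-square sizes of 0.107 at odds ratios of 1 and 1.5 are within about two Monte Carlo errors of 0.10 and match the stratified test closely. No stated figure is wrong.
- *The QOL models ignore the factors.* The plan permits them; it does not require them.
- *All the error bars are too wide.* Only the QOL contrasts have planned between-arm intervals. For PRO-CTCAE the issue is conservative p-values, and for discontinuation the planned intervals are one per arm.

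**What to change.** 1. **Section 14.1.4.** For the two stratification factors, change *may* to *will*: both enter as fixed effects in every QOL mixed model, not only the fatigue model. Keep other covariates for sensitivity analyses and name them in advance.
2. **Section 13.7.** Compare the PRO-CTCAE proportions (scores above 0, scores of 3 or more, unadjusted and baseline-adjusted) with a Mantel-Haenszel test stratified by platinum status and visceral metastasis, as 13.6 does for response. Use an exact stratified version when counts are sparse. Keep the unstratified test as a sensitivity analysis.
3. **1-year discontinuation.** No change is needed on this ground.

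The cost is wording only. Both factors are recorded at randomisation, so no new data or patients are needed. The downside is one degree of freedom per factor and exact stratified tests for rare items. If the factors are not prognostic, the simulated power is 75.1% stratified against 75.8% unstratified, a difference of about one Monte Carlo error.

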13.8 Study Monitoring

Data for this study will be submitted via the Data Mapping Utility (DMU). Cumulative protocol- and patient-specific data will be submitted weekly to CTEP electronically via the DMU. DMU Light reporting consists of Patient Demographics, On/Off Treatment Status, Abbreviated Treatment and Course information, and Adverse Events as applicable. Instructions for setting up and submitting data via DMU are available on the CTEP Website: (<https://ctep.cancer.gov/protocolDevelopment/dmu.htm>).

Note: All adverse events (both routine and serious) that meet the protocol mandatory reporting requirements must be reported via DMU in addition to expedited reporting of serious adverse events via CTEP-AERS.

The study team and DSMB will monitor the study for safety and whether the trial is meeting its accrual goals in a satisfactory manner. Monthly reports summarizing the adverse events will be generated and reviewed by the study. If at any time after 20 patients are 30% or more of the patients experience a grade 3 or higher AE, accrual will be suspended and the study team will review the adverse event data. In collaboration with CTEP, a decision will be made whether to resume accrual with the original treatment, modify the treatment and resume accrual, or close the study to accrual due to an unacceptable adverse event rate.

Note: Serious adverse events must be submitted via CTEP-AERS per protocol guidelines.

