9.2 CTCAE Routine Reporting Requirements

In addition to the solicited adverse events listed in [Section 9.1](#), the following table outlines the combinations of time points, grades and attributions of AEs that require routine reporting to the Alliance Statistics and Data Center. Questions about routine reporting should be directed to the Data Manager.

Combinations of CTCAE Grade & Attribution Required for Routine AE Data Submission on Case Report Forms (CRFs)

Attribution	Grade 1	Grade 2	Grade 3	Grade 4	Grade 5
Unrelated			a	a	a
Unlikely			a	a	a
Possible			a, b	a, b	a, b
Probable			a, b	a, b	a, b
Definite			a, b	a, b	a, b

- a) **Adverse Events: Other CRF** - Applies to AEs occurring between registration and within 30 days of the patient's last treatment date, or as part of the Clinical Follow-Up Phase.
- b) **Adverse Events: Late CRF** - Applies to AEs occurring greater than 30 days after the patient's last treatment date.

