9.3 Expedited Adverse Event Reporting (CTEP-AERS)

Investigators are required by Federal Regulations to report serious adverse events as defined in the table below. The descriptions and grading scales found in the NCI Common Terminology Criteria for Adverse Events (CTCAE) version 5 will be utilized for AE reporting. The CTCAE is identified and

located on the CTEP website at: ctep.cancer.gov/protocolDevelopment/electronic_applications/ctc.htm. All appropriate treatment areas should have access to a copy of the CTCAE. All reactions determined to be “reportable” in an expedited manner must be reported using the Cancer Therapy Evaluation Program Adverse Event Reporting System (CTEP-AERS).

For further information on the NCI requirements for SAE reporting, please refer to the ‘NCI Guidelines for Investigators: Adverse Event Reporting Requirements’ document published by the NCI.

Note: All deaths on study require both routine and expedited reporting regardless of causality. Attribution to treatment or other cause should be provided.

9.3.1 Late Phase 2 and Phase 3 Studies: Expedited Reporting Requirements for Adverse Events that Occur on Studies under an IND/IDE within 30 Days of the Last Administration of the Investigational Agent/Intervention^{1,2}

FDA REPORTING REQUIREMENTS FOR SERIOUS ADVERSE EVENTS (21 CFR Part 312)

NOTE: Investigators **MUST** immediately report to the sponsor (NCI) **ANY** Serious Adverse Events, whether or not they are considered related to the investigational agent(s)/intervention (21 CFR 312.64)

An adverse event is considered serious if it results in **ANY** of the following outcomes:

- 1) Death
- 2) A life-threatening adverse event
- 3) An adverse event that results in inpatient hospitalization or prolongation of existing hospitalization for ≥ 24 hours
- 4) A persistent or significant incapacity or substantial disruption of the ability to conduct normal life functions
- 5) A congenital anomaly/birth defect.
- 6) Important Medical Events (IME) that may not result in death, be life threatening, or require hospitalization may be considered serious when, based upon medical judgment, they may jeopardize the patient or subject and may require medical or surgical intervention to prevent one of the outcomes listed in this definition. (FDA, 21 CFR 312.32; ICH E2A and ICH E6).

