9.3.4 Additional Instructions or Exclusions to CTEP-AERS Expedited Reporting Requirements

All adverse events reported via CTEP-AERS (i.e., serious adverse events) should also be forwarded to your local IRB.

Alliance A032002 uses a drug under a CTEP IND. The reporting requirements for investigational agents under a CTEP IND should be followed for all agents (any arm) in this trial.

Treatment expected adverse events include those listed in Section 10.0 and in the package insert. CTEP-AERS reports should be submitted electronically.

Exclusions

≤ Grade 4 hematosuppression and hospitalization resulting from such do not require CTEP-AERS, but should be submitted as part of study results.

Grade 1-3 nausea or vomiting and hospitalization resulting from such do not require AERS reporting, but should be reported via routine AE reporting

Grade 3 nausea or vomiting does not require AERS reporting, but should be reported via routine AE reporting.

Death

Death due to progressive disease should be reported as Grade 5 “Disease progression” in the system organ class (SOC) “General disorders and administration site conditions.” Evidence that the death was a manifestation of underlying disease (e.g., radiological changes suggesting tumor growth or progression: clinical deterioration associated with a disease process) should be submitted.

Any death occurring within 30 days of the last dose, regardless of attribution to the investigational agent/intervention requires expedited reporting within 24 hours.

Any death occurring greater than 30 days after the last dose of the investigational agent/intervention requires expedited reporting within 24 hours only if it is possibly, probably, or definitely related to the investigational agent/intervention.

Pregnancy loss and neonatal death

Pregnancy loss is defined in CTCAE as “Death in utero.” Any Pregnancy loss should be reported expeditiously, as Grade 4 “Pregnancy loss” under the Pregnancy, puerperium and perinatal conditions SOC. A Pregnancy loss should NOT be reported as a Grade 5 event under the Pregnancy, puerperium and perinatal conditions SOC, as currently CTEP-AERS recognizes this event as a patient death.

A neonatal death should be reported expeditiously as Grade 4, “Death neonatal” under the General disorders and administration SOC.

New Malignancies

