13.0 STATISTICAL CONSIDERATIONS

13.1 Study Design

This is a prospective multicenter, randomized, open-label, phase 2 study evaluating whether the addition of radiation therapy to immunotherapy improves tumor response rate compared to treatment with immunotherapy alone in patients with platinum ineligible/refractory metastatic urothelial cancer. Allocation to the two study arms will be performed using stratified randomization as described in Section 4.6. Patients will be randomized 1:1 to immunotherapy (Arm A) or to immunotherapy plus radiation (Arm B). This trial is a superiority trial with the primary endpoint of tumor response. One formal interim analysis will be conducted for futility after 50% of the patients have been followed for 6 months after randomization; accrual will not be suspended for the interim analysis.

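### The Section 13.8 accrual-suspension rule counts any-cause grade 3+ AEs over both arms together, so disease deaths can trigger it and, in a different setting, Arm B toxicity can be diluted

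*Combined protocol and SAP*

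**What the plan says.** Section 13.8 (Study Monitoring) gives one numerical safety rule. It opens with "If at any time after 20 patients are 30% or more of the patients", and its operative words are "30% or more of the patients experience a grade 3 or higher AE, accrual will be suspended". A review by the study team follows. Together with CTEP, accrual is then resumed unchanged, resumed with modified treatment, or closed. The rule does not mention arm, attribution, observation window or any excluded event. A word is missing, so it is unclear whether the 20 patients, and the denominator after them, are enrolled, treated or evaluable.

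Other sections determine which events can enter the count:

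- Section 9.3.4: "Death due to progressive disease should be reported as Grade 5".
- Section 9.3: "All deaths on study require both routine and expedited reporting regardless of causality".
- Section 9.2: grade 3 to 5 AEs of any attribution go on one form, which "Applies to AEs occurring between registration and within 30 days of the patient's last treatment date" or falls in the clinical follow-up phase. The late form, for events after those 30 days, takes only events that are at least possibly related.
- Section 13.7: AEs are tabulated by arm at analysis. "The primary summary will be regardless of attribution", and a second summary covers events at least possibly related to treatment.

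Section 13.8 also provides for safety monitoring by the study team and DSMB: "Monthly reports summarizing the adverse events will be generated and reviewed by the study". It states no arm-level or related-only threshold.

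**The concern.** In a trial randomized 1:1, the patients in a sentence about all patients means both arms. The word pooled does not appear, but that is the plain reading. Two separate consequences follow.

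1. **Specificity.** Metastatic urothelial carcinoma has a high death rate. If disease deaths count as grade 3+ events, the cumulative proportion rises with follow-up whatever the treatment does, and accrual may be suspended for the disease itself.
2. **Sensitivity.** The safety question is what radiotherapy adds. Under equal allocation the pooled proportion is the mean of the two arm proportions, so a high rate in Arm B can be offset by a low rate in Arm A.

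At stake are an avoidable halt in a trial with about 30 months of planned accrual, and a safety trigger that does not look at the arm carrying the added risk.

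**Working it through.** The plan states no trigger probability for this rule, so there is no figure to reproduce.

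**Inputs from the documents.** Threshold 30%, from 20 patients (13.8). Allocation 1:1 (13.1). Target accrual 144 (13.4) at 5 per month (13.5), so accrual lasts 144/5 = 28.8 months, consistent with the stated 30 or so. Median OS on pembrolizumab 10.3 months, from the phase III trial described in Section 1.1.

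**Assumptions.** Survival is exponential. The grade 3+ rates by arm and the share of deaths recorded as AEs are shown as ranges, because the documents give neither.

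**1. Deaths alone.** The hazard is λ = ln 2/10.3 = 0.0673 per month. By 6 months a patient has died with probability 1 − 2^(−6/10.3) = 33%. At calendar month t, patient i has been followed for t − i/5 months. The expected proportion counted is the share f times the mean of 1 − exp(−λ(t − i/5)) over enrolled patients. That mean is 0.309 at month 12 (60 enrolled) and 0.555 at month 28.8 (144 enrolled).

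The last column comes from simulation: uniform accrual, rule checked monthly during accrual once 20 are enrolled, denominator all enrolled patients.

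| Share of deaths counted (f) | Expected proportion at end of accrual | Expected proportion reaches 30% | Trials triggered |
|---|---|---|---|
| 100% | 0.555 | month 11.4 (56 enrolled) | about 100% |
| 75% | 0.75 × 0.555 = 0.416 | month 16.8 (83 enrolled) | about 100% |
| 50% | 0.50 × 0.555 = 0.278 | month 30.4, after accrual | about 36% |
| 25% | 0.25 × 0.555 = 0.139 | not reached | 0% |

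If half of deaths count and 15% of patients also have a non-fatal grade 3+ event within 3 months, about 99% of trials trigger, at a median of month 14 to 15.

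**2. Dilution, with no deaths counted.** The pooled rate is (pA + pB)/2. Rates of 15%/40%, 10%/45% and 5%/50% all give 27.5%, below the threshold. In counts, 3/20 + 8/20 = 11/40 = 27.5% does not trigger with Arm B at 40%. Nor does 0/20 + 11/20 = 11/40, with Arm B at 55%.

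Chance crossings still occur when the rule is checked repeatedly. At true rates of 10%/45%, with monthly checks:

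| Version of the rule | Trials triggered |
|---|---|
| Pooled, events spread over the first 3 months | about 44% |
| Pooled, events counted at once | about 74% |
| Arm B alone | over 99% |
| Pooled, 3-month lag, 25% of deaths also counted | about 98% |

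The 44% depends on modelling detail: similar set-ups gave 34% to 43%. The lag matters because recent enrollees enter the denominator before they can have an event, and Section 13.8 does not say whether they should.

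**3. Dependence on the control rate.** With the lag and no deaths, the pooled rule triggers in about 80% of trials at 20%/45% and 92% at 25%/45%. Dilution is serious only when the Arm A rate is low.

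**The case against.** **How many deaths count.** Deaths more than 30 days after treatment may never enter the count. The late form in Section 9.2 takes only related events, and Section 9.3.4 asks for expedited reports of such deaths only if related. Patients leave treatment once they progress without benefit (12.1, 12.2), so many disease deaths could fall outside the window. This stands in part. Section 9.3 and the follow-up wording in 9.2 point the other way, so the share is unknown. A reader might infer that the rule will probably halt accrual on background deaths. The documents do not support that: across the possible shares the result runs from 0% to 100%.

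**Whether both faults can hold at once.** A reader might infer that the rule is both unspecific and insensitive, and so would stay silent on Arm B toxicity. That goes too far. Counting even a quarter of deaths, which alone never trigger the rule, lifts the 10%/45% case to about 98%. Dilution needs few counted deaths and a low Arm A rate, and nothing in the documents supports a 10% any-cause rate in this population. Oversight by the DSMB, monthly AE reports and expedited reporting also continue when the rule is not met.

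**All-cause counting as a choice.** In an open-label trial, a trigger limited to related events depends on investigators' attribution. All-cause counting avoids that and matches the primary summary in Section 13.7. This stands. It does not justify counting progression deaths or combining the arms.

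**Consequence.** Suspension is automatic but leads to review, and accrual may resume with the original treatment. This also stands.

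**Conclusion.** The concern holds as two conditional faults. As worded, the rule admits deaths from progression. At a 10.3-month median OS these alone would suspend accrual in nearly every trial if three quarters or more are counted, in about a third if half are, and in none if a quarter are. Separately, with few deaths counted and a low control-arm rate, pooling weakens detection of toxicity confined to Arm B: about 44% to 74% of trials trigger at 10%/45%, against over 99% for Arm B alone. A pooled crossing also does not show which arm caused it.

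These sizes rest on exponential survival, steady accrual, monthly checks and assumed AE rates. The structural points do not: no arm, no exclusion and no defined denominator. Existing oversight limits the harm to an avoidable pause or a less informative trigger, so this is a low-cost improvement worth making, not a flaw that invalidates the safety monitoring.

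**What to change.** Revise the sentence in Section 13.8 to:

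- apply the existing 30% threshold separately by arm, at least to Arm B;
- leave Grade 5 Disease progression out of the count;
- state the denominator (enrolled, treated or evaluable), any minimum observation time, and the number of patients in an arm from which the rule starts.

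Reconcile Sections 9.2, 9.3 and 9.3.4 on deaths more than 30 days after treatment. Give the DSMB all-cause and at-least-possibly-related tables by arm. Whether the trigger itself should be limited to related events is the sponsor's choice.

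No new data are needed. AEs are recorded with attribution, Section 9.3.4 already asks for evidence that a death was due to disease, and Section 13.7 already plans by-arm summaries.

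The cost is more early chance crossings with smaller denominators. At a true rate of 15%, the chance of 6 or more events in 20 patients is 6.7%. If the rule started at 10 patients in an arm, the chance of 3 or more would be 1 − 0.85^10 − 10(0.15)(0.85^9) − 45(0.15²)(0.85^8) = 1 − 0.197 − 0.347 − 0.276 = 18%. Starting at 20 patients in the arm keeps it at 6.7% at the first check, at the price of a later start. In return, at a true Arm B rate of 45%, the threshold is met with probability 95% at 34 Arm B patients and over 99% at 72.
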